### 11.3.2 Statistical Methods

The baseline value for clinical laboratory tests will be the last non-missing measurement on or before the day of the first dose of study drug. Values on Day 1 must also be before

the time of first dose if time is available. The same baseline value will be used for changes at Treatment Period visits and changes at Post-Treatment Period visits.

Changes from baseline to each post-baseline visit, including applicable post-treatment visits, will be summarized. Each protocol-specified laboratory parameter will be summarized with the sample size, baseline mean; visit mean; and change from baseline mean, standard deviation, minimum, median, and maximum.

Individual changes in the laboratory parameters listed in Section 11.3.1 will be tabulated using shift tables. Laboratory data values will be categorized as low, normal, or high based on normal ranges of the laboratory used for each sample. Shift tables from baselineto minimum value and maximum value during the Treatment Period will be created. For each parameter, the shift tables will cross tabulate the frequency of subjects with baseline values below/within the normal range to maximum above the normal range and with baseline values within/above the normal range to minimum below the normal range.

The laboratory parameters listed in Table 10 will be assigned a toxicity grade of 1, 2, 3, or 4. The number and percentage of subjects with a maximum toxicity grade of 1, 2, 3 or 4 will be tabulated. To be counted, the post-baseline value must have a toxicity grade that is more extreme than the toxicity grade corresponding to the baseline value. For each laboratory parameter in Table 10, the summary will also include the number and percentage of subjects with a maximum of at least grade 3. A listing of all relevant laboratory parameters will be provided for each subject who had an increase to grade 2 or higher for any laboratory variable in Table 10.

For CKD 3B and 4 subjects at screening, laboratory calculated eGFR by MDRD at Screening, EOT, and Post Treatment Week 4 will be summarized by mean, sd, minimum, maximum, median and interquartile range as well as by a box-plot.

CKD categorization at EOT is defined according to eGFR and requirement of dialysis in Table 4. For CKD 3B and 4 subjects at screening, number and percentage of subjects

changing in CKD stage (improvement, no change, or decline) between screening and EOT will also be summarized and graphed by treatment arm. For CKD 3B and 4 subjects at screening, a listing will be provided for subjects with CKD stage worsening based on any eGFR criteria or initiated dialysis treatment during the treatment and post treatment period. A separate listing will also be provided for subjects not on dialysis prior to screening while started dialysis post screening.

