**Figure 1. Study Schematic**

### 4.3 Sample Size

It is anticipated that approximately 120 HCV GT1 – 6 infected subjects with chronic renal impairment, with compensated cirrhosis or without cirrhosis, who are either HCV TN or TE with IFN or pegIFN with or without RBV, or SOF plus RBV with or without pegIFN will be enrolled in the study. No formal hypothesis is being tested. If the observed SVR12 rate in this study is 97% among 120 HCV GT1 – 6 renally impaired subjects, then the half-width of the 2-sided 95% confidence interval (CI) using the normal approximation to the binomial distribution is 0.031 (nQuery Advisor, Version 8.0, Statistical Solutions, Ltd., Boston, MA).

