### **6.2 Definition of Analysis Windows**

For efficacy analyses of HCV RNA, the time windows specified in [Table 1](#) and [Table 2](#) describe how efficacy data are assigned to protocol-specified time points during the Treatment and Post-Treatment Periods, respectively. All time points and corresponding time windows are defined based on the date/time of blood sample collection.

For safety laboratory data, PRO data, Child Pugh score and vital sign data, the time windows specified in [Table 1](#) and [Table 3](#) describe how data are assigned to protocol-specified time points.

If more than one assessment is included in a time window, the assessment closest (except in analyses of SVR) to the nominal time will be used. If there are two observations equally distant to the nominal time, the latest one will be used in analyses. For analyses of SVR (e.g., SVR12), the last value in the window will be used.

If multiple measurements are made on the same day for a safety laboratory parameter or a vital sign parameter, the average of the values will be used to calculate descriptive statistics and in analyses of the mean change from baseline. For summaries of shifts from baseline and potentially clinically significant values, multiple values on the same day will not be averaged; all values will be considered for these analyses.

**Table 1. Analysis Time Windows for HCV RNA and Resistance Endpoints, Safety Laboratory and Vital Sign Measurements, Child Pugh Scores and PRO Instruments (Treatment Period)**

Scheduled Visit	Nominal Day (Study Day)	Time Window (Study Day Range)
Day 1/Baseline a	1	≤ 1 a
Week 4	28	2 to 42
Week 8	56	43 to 70
Week 12 b,c	84	71 to 98
Week 16 c	112	99 to 126
Final Treatment Visit d	2 to ≤ 2 days after last dose of study drug	

a. Day of first dose of study drug.

b. For 12-week and 16-week treatment duration only.

c. For 16-week treatment duration only.

d. The last value within the window will be used to define the Final Treatment Visit value. The upper bound of this Final window is Study Drug End Day 2. Study Drug End Day 0 is defined as the day of the last dose of study drug.

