## **11.0 Safety Analysis**

### **11.1 General Considerations**

Safety analyses will be performed using the safety population. Data will be summarized overall (across all arms).

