### **11.3 Analysis of Laboratory Data**

Data collected from the central and local laboratories, including additional laboratory testing due to a serious AE, will be used in all analyses.

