#### **11.3.1 Variables and Criteria Defining Abnormality**

Hematology variables to be summarized include: hematocrit, hemoglobin, red blood cell (RBC) count, white blood cell (WBC) count, neutrophils, bands, lymphocytes, monocytes, basophils, eosinophils, platelet count, reticulocyte count, prothrombin time (PT), international normalized ratio (INR), and activated partial thromboplastin time (aPTT).

Chemistry variables to be summarized include: blood urea nitrogen (BUN), creatinine, total bilirubin, direct and indirect bilirubin, alanine aminotransferase (ALT), aspartate aminotransferase (AST), alkaline phosphatase, sodium, potassium, calcium, inorganic phosphorus, total protein, glucose, albumin, chloride, bicarbonate, magnesium, gamma-glutamyl transferase (GGT), creatinine clearance (calculated using Cockcroft-Gault), and eGFR by MDRD.

The definitions of toxicity grades for laboratory parameters are presented in [Table 10](#).

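### The general laboratory mean-change and shift tables pool subjects on and off dialysis for analytes that dialysis alters, which dilutes any change confined to subjects off dialysis

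*SAP*

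**What the plan says.** Section 11.1 sets the level of presentation for safety: "Data will be summarized overall (across all arms". The chemistry list in Section 11.3.1 includes creatinine, BUN, potassium, inorganic phosphorus and bicarbonate, and ends with "creatinine clearance (calculated using Cockcroft-Gault), and eGFR by MDRD".

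For all these parameters Section 11.3.2 says "Changes from baseline to each post-baseline visit, including applicable post-treatment visits, will be summarized". It adds shift tables from baseline to the lowest and highest value in the Treatment Period. Neither output is split by dialysis or CKD stage.

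Table 4 puts subjects who require dialysis in Stage 5, so they are part of the study population. Section 7.1 derives dialysis at screening from the dialysis eCRF, counting any dialysis started before the Day 1 visit. Section 10.6 uses a four-level CKD variable for SVR12 that separates Stage 5 with and without dialysis.

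Section 11.3.2 also plans renal outputs for subjects at Stage 3b or 4 at screening:
- an eGFR summary with box-plot;
- a summary of CKD-stage change;
- a listing of stage worsening or dialysis initiation.

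A further listing covers subjects who start dialysis after screening.

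**The concern.** Dialysis acts directly on creatinine, BUN, potassium, phosphorus and bicarbonate. eGFR by MDRD and creatinine clearance by Cockcroft-Gault are computed from serum creatinine, so in a subject on dialysis they do not describe the subject's own kidney function. Averaging them with values from subjects who still rely on their own kidneys gives a figure with no clear meaning for either group.

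The study's population is defined by renal impairment, and safety is a primary objective. A reader will look to these tables to see whether renal laboratory values or electrolytes moved during treatment. If they moved only in subjects off dialysis, the pooled mean understates it, and nothing elsewhere in the SAP recovers the size of the change for most of these analytes.

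**Working it through.** **The plan's only design figure.** Section 4.3 assumes an SVR12 "rate in this study is 97% among 120 HCV GT1 – 6 renally impaired subjects" and says "the half-width of the 2-sided 95% confidence interval (CI) using the normal approximation to the binomial distribution is 0.031". Check: 1.96 × √(0.97 × 0.03 / 120) = 0.0305, which rounds to 0.031. The figure is reproduced. It concerns SVR12, and the present point does not depend on it.

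**Which outputs cover which subjects and analytes.**
- eGFR, Stage 3b/4: dedicated summary, stage-change summary and listings, plus the pooled tables.
- eGFR, Stage 5 not on dialysis: pooled tables only, plus the listing of new dialysis starts.
- Creatinine, creatinine clearance and potassium, all stages: pooled mean-change and shift tables, plus toxicity grades from Table 10, which are also pooled.
- BUN, phosphorus and bicarbonate, all stages: pooled mean-change and shift tables only, because Table 10 has no row for them.

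Tabulating by arm would not separate the groups. Section 4.2 defines Arms A, B and C by genotype, cirrhosis and treatment experience, not by dialysis.

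**Dilution of the mean.** Let d be the share of subjects on dialysis and δ a mean change that occurs only off dialysis. Then

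pooled mean change = (1 − d) × δ + d × 0 = (1 − d) × δ.

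The SAP gives no number or cap for dialysis subjects, so d is assumed over a range, with all 120 planned subjects contributing a value:

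| On dialysis (assumed) | d | Fraction of δ shown, 1 − d |
|---|---|---|
| 20 of 120 | 0.167 | 83% |
| 40 of 120 | 0.333 | 67% |
| 60 of 120 | 0.500 | 50% |
| 80 of 120 | 0.667 | 33% |

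**Spread.** Let r be the ratio of the SD of change on dialysis to that off dialysis. With equal group means, dialysis subjects supply this share of the pooled variance:

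d·r² / (d·r² + 1 − d).

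| On dialysis (assumed) | r = 1 | r = 2 | r = 3 |
|---|---|---|---|
| 20 of 120 | 17% | 44% | 64% |
| 40 of 120 | 33% | 67% | 82% |
| 60 of 120 | 50% | 80% | 90% |
| 80 of 120 | 67% | 89% | 95% |

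At r = 1 the dialysis group contributes only its head count; at r = 3 it dominates. The SAP gives neither d nor r, so the second table shows only how wide the possibilities are.

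**The case against.** The strongest reply is that the SAP already analyses kidney function where it can be measured. The eGFR and stage-change summaries are restricted to Stage 3b/4, and worsening and new dialysis are listed. That stands for eGFR in Stage 3b/4. It does not reach the other analytes or Stage 5 subjects off dialysis, and it does not stop eGFR and creatinine clearance on dialysis from entering the pooled mean change.

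It is also fair that the study is descriptive ("No formal hypothesis is being tested") and uncontrolled. A split would not isolate a drug effect; it would only make a change in subjects off dialysis visible.

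Several stronger readings are tempting but not supported:

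- **Dialysis, rather than study drug, determines these results.** This would need the dialysis share and the laboratory SDs, and the SAP gives neither. The variance share above runs from 17% to 95% over plausible inputs.
- **A subject on dialysis could appear to change CKD stage when creatinine moves.** Table 4 keeps anyone requiring dialysis in Stage 5 whatever the eGFR, and stage change is tabulated only for Stage 3b/4.
- **Samples before and after a dialysis session on one day are averaged for means and taken as extremes for shifts.** Section 6.2 does say of shifts that "multiple values on the same day will not be averaged; all values will be considered for these analyses", and Section 11.3 admits local results: "Data collected from the central and local laboratories, including additional laboratory testing due to a serious AE, will be used in all analyses". But nothing says two such samples are drawn on one day. Timing of draws relative to dialysis may be set in the protocol, which is not at hand.
- **The shift tables will fill with false creatinine and BUN shifts.** Section 11.3.2 counts an upward shift only from a baseline below or within the normal range, so a subject already high cannot be counted. Potassium, phosphorus and bicarbonate are less protected, but the SAP gives no basis for a size.

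**Conclusion.** The point holds as a limitation of presentation. The general tables mix two groups in whom these analytes mean different things, and the dedicated renal summaries fill the gap only for eGFR and CKD stage in Stage 3b/4. A mean change confined to subjects off dialysis would show at 83% to 33% of its size for 20 to 80 of 120 on dialysis. This rests on three assumptions: the dialysis share, no mean change on dialysis, and all 120 subjects contributing. The effect on variance is left open because its inputs are not in the SAP.

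The SVR12 analysis is unaffected, and no statement in the SAP is contradicted. The change is worth making because it is cheap and the variable it needs is already derived.

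**What to change.** In Section 11.3.2:

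1. Present the mean-change and shift tables for creatinine, BUN, potassium, phosphorus and bicarbonate by dialysis status at Day 1 (on or not on dialysis), and keep the overall column. Use the dialysis variable that Section 7.1 already derives from the eCRF.
2. Limit mean change in eGFR and creatinine clearance to subjects not on dialysis at Day 1, using values up to any start of dialysis. This brings in Stage 5 subjects not on dialysis, whom the Stage 3b/4 summary omits.

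The cost is a few lines of SAP text and extra table columns, with no new data collection. The downside is smaller groups in each column and so less precise means, which is why the overall column should stay.

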### **Assessment of Hepatic Laboratory Values**

The number and percentage of subjects with laboratory values meeting the following criteria during treatment will be summarized:

- Post-nadir (preceding value is lower than the subsequent value) ALT  $> 5 \times$  ULN (regardless of grade change);
- Total bilirubin  $\geq 2 \times$  ULN and  $>$  baseline (i.e., a post-baseline value must be more extreme than the baseline value to be considered);
- Post-nadir ALT  $> 3 \times$  ULN and total bilirubin  $> 2 \times$  ULN;
- Post-nadir ALT  $> 3 \times$  ULN and total bilirubin  $\leq 2 \times$  ULN.

Four listings (one for each bullet above) of all liver function tests including ALT, AST, total, indirect and direct bilirubin, ratio of direct to total bilirubin, and alkaline phosphatase values will be provided for each subject who met the criterion defined above.

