#### **Final Treatment Value**

The final treatment value is defined as the last non-missing measurement collected after Study Day 1 and on or before Study Drug End Day 2.

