Note: For all windows, data must be on or before Study Drug End Day 2. The result closest to the scheduled time point will be used. PRO instruments are collected at Day 1, Week 4, Week 12 (Arm C only) and End of Treatment Visit, which can be at Week 8, 12 or 16 depending on treatment assignment, or Premature Discontinuation Visit.

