**Table 2. Analysis Time Windows for HCV RNA and Resistance Endpoints (Post-Treatment Period)**

Scheduled Visit a	Nominal Day (Study Drug End Day)	Time Window (Study Drug End Day Range)
Post-Treatment Week 4	28	3 to 56
Post-Treatment Week 12	84	57 to 126
Post-Treatment Week 24	168	127 to 999
SVR 4 b	28	3 to 56
SVR 12 b	84	57 to 126
SVR 24 b	168	127 to 210

a. Post-Treatment Visits are applicable for subjects who received at least one dose of study drug.

b. For SVR windows, the last value in the window will be used.

Note: The result closest to the scheduled time point will be used, except for SVR4, SVR12, and SVR24. For all windows, data must occur after Study Drug End Day 2. Study Drug End Day 0 is defined as the day of the last dose of study drug.

**Table 3. Analysis Time Windows for Safety Laboratory and Vital Sign Measurements, Child Pugh Scores and PRO Instruments (Post-Treatment Period)**

Scheduled Visit a	Nominal Day (Study Drug End Day)	Time Window (Study Drug End Day Range)
Post-Treatment Week 4	28	3 to 56
Post-Treatment Week 12	84	57 to 126
Post-Treatment Week 24	168	127 to 999
Final Post-Treatment Visit b	> 2 days after last dose of study drug	

a. Post-Treatment Visits are applicable for subjects who received at least one dose of study drug.

b. The last value within the Post-Treatment Period window will be used to define the Final Post-Treatment visit value. The lower bound of this Final window is Study Drug End Day 3. Study Drug End Day 0 is defined as the day of the last dose of study drug.

Note: The result closest to the scheduled time point will be used. For all windows, data must occur after Study Drug End Day 2. Vital signs are collected at every post-treatment visit; hematology, chemistry and coagulation panels are collected at PTW4 or PT D/C (if subject discontinued prior to PTW4). PRO instruments and Child Pugh Scores are collected at PTW12 and PTW24 (or PT D/C).

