#### **11.2.1 Treatment-Emergent Adverse Events**

Treatment-emergent AEs are defined as any AE with an onset date that is after the first dose of study drug and no more than 30 days after the last dose of study drug. Events where the onset date is the same as the study drug start date are assumed to be treatment-emergent. If an incomplete onset date was collected for an AE, the event will be assumed to be treatment-emergent, unless there is other evidence that confirms that the event was not treatment-emergent (e.g., the event end date was prior to the study drug start date).

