### **Hepatic Laboratory Abnormalities of Interest**

Among the events assessed under "Assessment of Hepatic Laboratory Values," the following criteria are of interest:

- Confirmed post-nadir ALT  $> 5 \times$  ULN;
- Post-nadir ALT  $> 3 \times$  ULN and a concurrent total bilirubin  $> 2 \times$  ULN with a direct bilirubin:total bilirubin ratio  $> 0.4$ .

To support the assessment of hepatic laboratory abnormalities of interest, the following potential events will be summarized:

- Confirmed post-nadir ALT  $> 5 \times$  ULN;
- Post-nadir ALT  $> 3 \times$  ULN and total bilirubin  $> 2 \times$  ULN and direct/total bilirubin ratio  $> 0.4$ .

Two listings (one for each bullet) of all liver function tests including ALT, AST, total, indirect and direct bilirubin, ratio of direct to total bilirubin, and alkaline phosphatase values will be provided for each subject who met the criterion defined above.

For the **assessments of hepatic laboratory values** and **hepatic laboratory abnormalities of potential interest**, the maximum ratio relative to the ULN will be used to determine if subjects meet any of the criteria listed above. The ALT and total bilirubin values do not need to be concurrent in order to meet the defined criteria in statistical summaries. For ALT, the post-baseline value must represent an increase from the first nadir (including baseline) to be counted. First nadir is defined as the last value prior to the first increase. For total bilirubin, a subject will be counted if the post-baseline laboratory value meets the above criteria regardless of the baseline laboratory value (i.e., the post-baseline laboratory value does not need to be worse than the baseline laboratory value), except where noted above. A confirmed post-nadir increase in ALT is defined as two consecutive values of ALT  $> 5 \times$  ULN after nadir, either both during treatment or at the final treatment measurement and the next consecutive post-treatment measurement. A single post-nadir ALT value of greater than  $5 \times$  ULN followed by lost to follow-up (no additional ALT values) also will be considered (i.e., will not require confirmation). The ratio of direct to total bilirubin will be calculated using the same date/time sample corresponding to the total bilirubin elevation.

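### The hepatic threshold summaries, read with the Day 2 limit in Section 6.2, omit elevations first measured later, and no other table pairs ALT with bilirubin

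*SAP*

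**What the plan says.** - **Hepatic criteria (SAP 11.3.2, Assessment of Hepatic Laboratory Values).** "The number and percentage of subjects with laboratory values meeting the following criteria during treatment will be summarized". The four criteria are post-nadir ALT > 5 × ULN; total bilirubin ≥ 2 × ULN and above baseline; post-nadir ALT > 3 × ULN with bilirubin > 2 × ULN; and the same ALT threshold with bilirubin ≤ 2 × ULN. Each has a listing confined to subjects who met it.
- **Abnormalities of interest (next subsection).** Two criteria are taken from the same events: "Among the events assessed under 'Assessment of Hepatic Laboratory Values,' the following criteria are of interest". Their two listings carry the same restriction. For confirmed ALT > 5 × ULN, a post-treatment ALT can serve only as the second value of a pair that starts at the final treatment measurement.
- **Shift tables (11.3.2).** These run from baseline to "minimum value and maximum value during the Treatment Period will be created".
- **Laboratory periods (Section 6).** The note to Table 1 says "For all windows, data must be on or before Study Drug End Day 2". The final treatment value is the "last non-missing measurement collected after Study Day 1 and on or before Study Drug End Day 2". For the post-treatment windows in Table 3, "For all windows, data must occur after Study Drug End Day 2". The Post-Treatment Week 4 window there is Days 3 to 56, nominal Day 28.
- **Adverse events (11.2.1).** Treatment-emergent means onset "no more than 30 days after the last dose of study drug".
- **Sampling (note to Table 3).** After treatment, "hematology, chemistry and coagulation panels are collected at PTW4 or PT D/C (if subject discontinued prior to PTW4").
- **Other laboratory outputs.** Section 11.3 brings central, local and SAE-driven tests into every analysis. The Table 10 grade summaries and the listing of increases to grade 2 or higher refer to post-baseline values and name no end of period. Mean-change tables include post-treatment visits.

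**The concern.** Liver injury that first shows in the blood a few days after dosing stops can be a treatment-emergent adverse event and yet be missing from the tables built to detect it. The count that matters most is the combined one, ALT > 3 × ULN with bilirubin > 2 × ULN, because no other table in the plan pairs the two. The data will exist, since a chemistry panel is scheduled after treatment and unscheduled work-up is to be used. The study also plans to enrol up to approximately 30 subjects with compensated cirrhosis.

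The plan looks past the end of treatment elsewhere. The listing of worsening CKD stage covers the treatment and post-treatment periods, and the Child-Pugh shift tables include post-treatment visits. No reason is given for a narrower hepatic count.

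**Working it through.** The plan states no figure on this point. Its one design figure, the SVR12 half-width of 0.031, reproduces (1.96 × √(0.97 × 0.03 / 120) = 0.0305) but plays no part here.

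**1. Where the hepatic period ends.** The hepatic subsection gives no day limit, so the limit has to be inferred. The definition of a confirmed ALT rise contrasts two values during treatment with a final treatment value followed by a post-treatment one. The first phrase therefore excludes post-treatment values. The final treatment value ends at Study Drug End Day 2, and Table 1 applies the same limit to safety laboratory data. The SAP offers no other boundary.

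**2. Compare the windows** (days after last dose).

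| Day of first elevation | Hepatic criteria, listings, shift tables | AE with onset that day |
|---|---|---|
| 0 to 2 | counted | treatment-emergent |
| 3 to 30 | not counted | treatment-emergent |
| 31 to 56 | not counted | not treatment-emergent |

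The mismatch is 30 − 2 = 28 days.

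**3. What is sampled there.** The Post-Treatment Week 4 window has 56 − 3 + 1 = 54 days. Days 3 to 30 are 28 of these (28/54 = 52%) and Days 31 to 56 are the other 26. Extending the hepatic tables to Day 30 would take in the nominal Day 28 draw but not a late one. If chemistry is drawn at every Table 1 visit (an assumption), the Week 4 draw is 1 of 3 scheduled post-baseline draws in Arm A, 1 of 4 in Arm B and 1 of 5 in Arm C.

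**4. A test case.** Take a subject first found abnormal 3 days after the last dose, with ALT 8 × ULN and bilirubin 4 × ULN.
- Hepatic criteria, abnormalities of interest, six listings, shift tables: not counted.
- Table 10: Grade 3 ALT (> 5 to 20 × ULN) and Grade 3 bilirubin (> 3 to 10 × ULN). If post-baseline includes post-treatment values and the baseline grades were lower, the subject enters both grade tables and the grade 2 or higher listing.
- Count of subjects with both ALT and bilirubin raised: not counted in any table.

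**5. Scale.** Wilson 95% intervals at N = 120 are 0.0 to 3.1% for 0/120 and 0.1 to 4.6% for 1/120 (0.8%). One missed case would do this to any table of this size, so it shows scale and says nothing about likelihood.

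**The case against.** The best defence is that each table does what its label says. An on-treatment table does not understate on-treatment events, and post-treatment ALT rises may reflect viral relapse, which is a reason to keep them out. The clinical event is also covered elsewhere: hepatic decompensation and failure have their own search, table and listing on the 30-day window, serious events are listed to the end of the study, and mean-change tables include post-treatment visits.

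Much of this stands, and it rules out several stronger readings that a reader might infer:

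- *That such a subject vanishes from all hepatic laboratory output.* The grade tables and the grade 2 or higher listing carry no stated Treatment Period limit, although the neighbouring shift tables do. They may well capture each elevation singly.
- *That any discontinuation visit is lost.* A visit on or before End Day 2 is counted.
- *That the two windows contradict each other.* They differ, which is a gap in coverage and not an inconsistency or a numerical error.
- *That the omission is informative because subjects who stop for toxicity tend to be sampled late.* This is plausible, but the SAP gives no visit timing that would show it.

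The defence does not answer the combined criterion. Separate ALT and bilirubin grades do not give a count of subjects with both, adverse-event tables do not apply laboratory thresholds, and mean changes dilute one subject's result. The relapse argument supports a separate row, not the absence of one.

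**Conclusion.** The point holds as a limited gap. Under the Section 6.2 limit, the hepatic threshold summaries, their listings and the shift tables omit an elevation first measured more than 2 days after the last dose. That leaves 28 days of the adverse-event window, and the scheduled Post-Treatment Week 4 chemistry, outside them. The material loss is the combined ALT and bilirubin count.

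This rests on two readings: that the treatment period in 11.3.2 ends at End Day 2, which is inferred, and that the Table 10 period is open, which is what the text leaves. If the sponsor intends otherwise on either, 11.3.2 should say so. How many subjects would be affected cannot be estimated from the SAP. The change is a cheap improvement, not the correction of an error.

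**What to change.** In Section 11.3.2:

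1. State that the existing hepatic rows cover values to Study Drug End Day 2, and keep them unchanged.
2. Add a separate post-treatment row and listing to the hepatic criteria and to the abnormalities of interest. Cover all values after End Day 2 through the Post-Treatment Week 4 or post-treatment discontinuation draw (Table 3 window, Days 3 to 56).
3. Within that row, flag values on Days 3 to 30 to match 11.2.1. A bare 30-day cut-off would still miss draws on Days 31 to 56.
4. State the period used for the Table 10 grade tables and the grade 2 or higher listing.

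The cost is SAP wording plus one row and one listing per summary, with no new data. The downside is that some post-treatment ALT rises will reflect relapse; the separate row keeps these apart from the on-treatment result.
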